5.4 Preparation and Administration of Study Drug

Avmacol[®] and placebo tablets will be shipped in bulk to UNC IDS [contact]) in 500 count bottles, which will be stored at 2-8°C in the refrigerator until needed. Prior to a participant's study visit, a 5-week supply of the investigational drug (Avmacol[®] or placebo) will be packaged in a smaller, labeled bottle to be picked up by study staff. The label will not indicate whether the bottles contain Avmacol® or placebo tablets. The study personnel will verify the number of tablets dispensed and record on the drug accountability form. The bottle of investigational drug will be stored in a small refrigerator used exclusively for this purpose at the study site until the designated visit. The investigational drug will be dispensed to the subject's caregiver at the time of the study visit (Baseline, Week 4, and Week 8 visits) in a freezer bag for transport with instructions to store the bottle in a home refrigerator. Subjects and caregivers will be advised to avoid taking the tablets with a heavy meal and to take by mouth at approximately the same time every day. If a subject is unable to swallow pills, the tablets may be crushed with a pill crusher or mortar and pestle and mixed with a soft food, such as applesauce. Of note, investigators at the Cullman Chemoprotection Center and others have successfully administered sulforaphane and its precursor, glucoraphanin, in a number of different formulations, both encapsulated and in various types of juices [43, 44, 46, 47, 105].

5.5 Subject Compliance Monitoring

Subjects' caregivers will be provided with a medication log to track daily dosing of the study medication. At Week 4, Week 8, and Week 12 visits, subjects and their caregivers will be instructed to return the medication log and any unused tablets to study staff, who will count the remaining tablets and address any discrepancies between remaining tablets and the medication log with the families. Compliance percentages will be recorded on a drug compliance form. For frequent missed doses, the study physician will discuss the importance of adherence to the recommended dosing regimen and will identify any potential barriers to compliance, providing support when possible.

5.6 Prior and Concomitant Therapy

Participants will be permitted to continue their usual regimen of medications, psychotropic and otherwise, during the study with the exception of chronic anti-inflammatory medications (e.g., ibuprofen, naproxen, corticosteroids), which may confound the treatment effects. Concomitant medication doses must be stable for 4 weeks prior to study enrollment and remain constant for the duration of the study, to the extent possible.

5.7 Packaging

Avmacol[®] will be shipped in bulk from Nutramax Laboratories, Inc. ([name]) to UNC IDS in boxes of bottles containing 500 tablets of Avmacol[©] each. The bottle labels will include: product name (Avmacol[®]), manufacturer (Nutramax Laboratories, Inc.), Quantity, Lot Number, Expiration Date, Study Name (Avmacol[®] for autism spectrum disorder), Institution (UNC), PI ([name]), IRB number, "Investigational Study Material," and "Caution: New Drug Limited by Federal Law to Investigational Use Only." For an example of labelling, please see section 7.3.7 of the IND application.

Matched placebo tablets will be manufactured and shipped from the University of Maryland Department of Pharmaceutical Sciences ([name]) to UNC IDS in boxes of HDPE plastic bottles containing 200 tablets each. The bottles will be individually labeled as described above.

5.8 Blinding of Study Drug (if applicable)

Subjects will be randomized by IDS pharmacy personnel using a random numbers list, and treatment assignment will not be disclosed to study staff. Avmacol[®] and placebo tablets will be similar in shape, size, and color, and the labels on bottles dispensed to study staff and families will not indicate treatment assignment. Blinding of treatment assignment for the study team and subjects will be maintained until after the conclusion of all data collection. In the event of a serious adverse event, a physician monitor who is not directly associated with the study (ie, an independent medical monitor) will determine if the SAE is potentially related to taking the study drug. If a possible association is suspected, the pharmacy will disclose treatment status to the medical monitor, and the event will be reviewed by the medical monitor and Data Safety Monitoring Board (DSMB) to determine if treatment discontinuation is warranted.

Receiving, Storage, Dispensing and Return

5.8.1 Receipt of Drug Supplies

Avmacol[®] will be shipped in bulk from Nutramax Laboratories, Inc. ([name]) to UNC IDS (IDS Pharmacy, [name]) in boxes of bottles containing 500 tablets of Avmacol[®] each. Matched placebo tablets will be shipped in bulk from the University of Maryland Department of Pharamceutical Sciences ([name]) to UNC IDS in boxes of bottles containing 200 placebo tablets each.

Upon receipt of the investigational drug/ placebo, an inventory will be performed and a drug receipt log filled out and signed by the IDS personnel accepting the shipment. IDS staff will count and verify that the shipment contains all of the items noted in the shipment inventory. Any damaged or unusable study drug in a given shipment (active drug or placebo) will be documented in the study files. The PI will notify the manufacturer of any damaged or unusable study drug that was supplied to the study site.

5.8.2 Storage

The investigational drug (Avmacol[®]) and placebo tablets will be stored at 2-8^oC in the refrigerator in UNC Investigational Drug Services (IDS) pharmacy prior to being dispensed to study staff in the week prior to the designated study visit. The study drug will be stored on site at the CIDD in a refrigerator used expressly for study drug storage until the study visit, at which time it will be dispensed to the participant's caregiver by the study team. Caregivers will be asked to store the bottle of study drug in a home refrigerator as a precautionary measure to preserve the integrity of the compound, though the manufacturer of Avmacol[®] reports stability at room temperature.

5.8.3 Dispensing of Study Drug

Study drug will be dispensed by UNC IDS to study staff in labeled bottles containing a 5-week supply (4 week supply plus 1 week buffer) of active drug or placebo tablets prior to baseline, week 4, and week 8 study visits. The study drug will be stored on site at the CIDD in a refrigerator used expressly for study drug storage until the study visit, at which time it will be dispensed to the participant's caregiver by the study team. Caregivers will be asked to transport the investigational drug in a freezer bag and store the bottle of study drug in a home refrigerator as a precautionary measure to preserve the integrity of the compound, though the manufacturer of Avmacol® reports stability at room temperature. Caregivers will be asked to record each administered dose on a medication log and to return the medication log and any unused study drug to study staff at the next visit. Study drug reconciliation will be performed at week 4, week 8, and week 12 study visits to document drug assigned, drug consumed, and drug remaining. This reconciliation will be logged on the drug accountability form, and signed and dated by the study personnel and study physician.

Return or Destruction of Study Drug

At the completion of the study, there will be a final reconciliation of drug shipped, drug consumed, and drug remaining. This reconciliation will be logged on the drug reconciliation form, signed and dated. Any discrepancies noted will be investigated, resolved, and documented prior to destruction of unused study drug by IDS. Drug destroyed on site will be documented in the study files.

6 Study Procedures

6.1 Pre-Screen Phone Call:

Prior to screening, potential participants will undergo a pre-screening assessment by telephone or direct clinical interview with study staff to determine if basic eligibility criteria are met. A written copy of the informed consent document will be provided by mail, electronically, or in person for the participant's caregiver to read prior to the screening visit.

6.2 Screening Visit:

The screening visit will take approximately 3 hours to complete. At screening, we will first obtain written informed consent from participants or their Legally Authorized Representatives (LAR). We anticipate that most subjects will not have capacity to provide informed consent themselves due to cognitive and/or communication deficits associated with ASD, though every effort will be

made to increase their participation in the consent/ assent process. For individuals under 18 years of age or those unable to consent due to significant cognitive or communication impairment, written assent for participation will be sought. An electronic, tablet-based interactive consent tool will be piloted to enhance participation in the consent process.

After written informed consent is obtained, diagnosis of autism spectrum disorder (ASD) will be confirmed by two measures: clinical review of the Diagnostic and Statistical Manual-5 (DSM-5) [1] ASD criteria and Autism Diagnostic Observation Schedule-2 (ADOS-2) total score [106]. The ADOS-2 is a semi-structured assessment of communication, social interaction, and repetitive behavior that is widely regarded as the gold standard of ASD diagnosis [106]. The ADOS-2 will be performed by a trained master's-level clinician, and DSM-5 diagnostic criteria for ASD will be assessed by a study physician with extensive experience in diagnosing ASD. ADOS-2 administration will be videotaped to permit clinician scoring after administration; the digital recording will be stored on a secure server than will be accessible only by authorized study personnel with a password. Individuals must meet criteria for a diagnosis of ASD based on both DSM-5 criteria (severity level 2 or 3) and ADOS-2 total score (\geq 8, exceeding the "autism" cut-off) to be eligible for participation. An abbreviated cognitive assessment using the Wechsler Abbreviated Intelligence Scales (WASI) two non-verbal subtests will be [107] obtained for the purposes of data analysis, though there is no cut-off intelligence quotient (IQ) score for study participation. A medical history will be obtained by the study physician, including current medical conditions, past medical history, surgical history, psychiatric history, past and current psychotropic medications, allergies, and current non-pharmacological treatments for ASD (e.g., speech therapy, occupational therapy, behavioral therapy). Caregivers will complete the Social Responsiveness Scale, Second Edition (SRS-2) [100], Repetitive Behavior Scale-Revised (RBSR) [102], and Aberrant Behavior Checklist- Community Edition (ABC) [103] for baseline characterization of social communication deficits, repetitive behaviors, and behavioral challenges. The study physician will complete the Clinical Global Impression Severity Scale (CGI-S) [104], a 7point rating scale of overall symptom severity. Baseline bloodwork will include a comprehensive metabolic profile (CMP), liver function tests (LFTs), thyroid stimulating hormone (TSH), and complete blood count (CBC) with white blood count differential. Participants will be given an OMNIGene-Gut stabilization kit to take home and use in the collection of a stool sample in the 48 hr prior to the scheduled Baseline visit. The research team will instruct the participant and caregiver in the collection of the stool sample and ask them to return it at the Baseline visit.

6.3 Baseline Visit (Week 0):

The baseline visit will take approximately 1.5 hr to complete. Prior to the baseline visit, the study physician will review safety labs drawn at the screening visit (CBC, CMP, LFTs, TSH) to ensure eligibility for participation. For individuals who meet all inclusionary and exclusionary criteria as described in sections 4.1 and 4.2, a baseline visit will be scheduled within 2 weeks of screening. Clinical outcome measures will again be obtained from caregivers, including the SRS-2, ABC, and RBSR. The study physician will complete the CGI-S to establish baseline clinical severity of ASD prior to intervention. Vital signs (height, weight, blood pressure, heart rate, and temperature) will be obtained by study staff. An adverse event log for baseline symptom assessment will be completed by the study physician. With specific written informed consent, participants will provide a saliva sample (approximately 2.6 mL total), either through expectoration into a special collection tube or through cheek swab (approximately 5 swabs). The de-identified saliva sample

will be stored in the UNC Biospecimen Repository for use in a possible future study of genetic markers associated with clinical response to sulforaphane. Participation in the storage of genetic material is not required for participation in the primary clinical trial. Participants will also return the stool sample in the OMNIGene-Gut stabilization kit, which is stable at room temperature for up to 60 days. The kit will be labeled with the date and participant PIN, securely packaged in a Styrofoam container, and mailed to the Cullman Chemoprotection Center at JHU (director, [name]) for storage in cryovials at -80^oC until all study samples have been collected.

Participants will be randomly assigned at baseline to receive either the active compound (Avmacol®) or identical placebo tablets. UNC IDS will be provided with a random table of numbers for randomization of participants, and both study staff and participants will remain blinded to treatment assignment. Study staff will retrieve the investigational product in labeled bottles from IDS and stored on site in a refrigerator at 2-8°C prior to the baseline visit. A 5-week supply of investigational drug will be dispensed to the participant and their caregiver in a labeled bottle by study staff at the visit, and they will be instructed to transport the bottle home in a freezer bag (supplied by study staff) and store the bottle in their home refrigerator to ensure compound stability (a precautionary measure; the manufacturer of Avmacol® reports stability at room temperature). They will be given detailed instructions for taking the medication and completing the medication log, which will be returned and reviewed at the participant's next visit. Caregivers will also be instructed to return any remaining tablets to the study staff at the following visit to determine adherence to the dosing protocol.

6.4 Week 2 Telephone Call:

The week 2 telephone call is expected to take approximately 20 minutes. The study physician will contact the subject's caregiver 2 weeks after the baseline visit to assess tolerability and general response. The adverse event log will be completed by the physician. Caregivers will be asked to report any changes in concurrent medications or non-pharmacological treatments since the previous study visit.

6.5 Week 4 Follow-Up Visit:

The week 4 visit will take approximately 1 hour. The subject and his caregiver will return to the clinic for a follow-up visit that will include measurement of vital signs (height, weight, blood pressure, heart rate, and temperature), caregiver completion of behavioral outcome measures (SRS-2, RBSR, and ABC), and clinician-rated CGI-Severity and CGI-Improvement scores. The adverse event log will also be completed by the study physician. Caregivers will be asked to report any changes in concurrent medications or non-pharmacological treatments since the previous study visit. The medication log and returned tablets will be reviewed/ counted for treatment compliance, and the next 5-week supply of investigational drug will be dispensed to the participant and his caregiver. Caregivers will be instructed to administer any unused tablets from the previous bottle before starting the new supply.

6.6 Week 8 Follow-Up Visit:

The week 8 visit will take approximately 1 hr. to complete. The patient and his caregiver will return to the clinic for a follow-up visit that will include measurement of vital signs (height, weight, blood pressure, heart rate, and temperature), caregiver completion of behavioral outcome measures (SRS-2, RBSR, and ABC), and clinician-rated CGI-Severity and CGI-Improvement scores.

The adverse event log will also be completed by the study physician. Caregivers will be asked to report any changes in concurrent medications or non-pharmacological treatments since the previous study visit. The medication log and returned tablets will be reviewed/ counted for treatment compliance, and the next 5-week supply of investigational drug will be dispensed to the participant and his caregiver. Caregivers will be instructed to administer any unused tablets from the previous bottle before starting the new supply. Participants will be given a new OMNIGene-Gut stabilization kit for collection of a stool sample at home in the 48 hr prior to the scheduled Week 12 visit. The research team will remind the participant and his caregiver of how to collect the sample and instruct to return it at the next visit.

6.7 Week 12 Follow-Up Visit:

The week 12 visit marks the end of the active treatment phase of the study and will take approximately 2 hr. to complete. The patient and his caregiver will return to the clinic for a follow-up visit that will include measurement of vital signs (height, weight, blood pressure, heart rate, and temperature), physical exam by the study physician, and repeat blood draw for safety monitoring (CMP, LFTs, TSH, and CBC with differential). Caregivers will complete behavioral outcome measures (SRS-2, RBSR, and ABC), and clinicians will assign CGI-Severity and CGI-Improvement scores. At this phase-ending visit, responder status will be assigned to those with a 10 point or greater reduction on the SRS-2 and CGI-Improvement score of 1 or 2 (very much or much improved). Partial responder status will be assigned to participants with a 10 point or greater reduction on the SRS-2 and a CGI-Improvement score of 3 (minimally improved). The adverse event log will also be completed by the study physician. Caregivers will be asked to report any changes in concurrent medications or non-pharmacological treatments since the previous study visit. The medication log and returned tablets will be reviewed/ counted for treatment compliance, and any remaining investigational drug will be collected by study staff and returned to IDS for disposal. Participants will also return a stool sample in the OMNIGene-Gut stabilization kit. The kit will be labeled with the date and participant PIN, securely packaged in a Styrofoam container, and mailed to the Cullman Chemoprotection Center at JHU (director, [name]) for storage in cryovials at -80°C until all study samples have been collected.

6.8 Week 16 Follow-Up Visit/ Study Termination:

The week 16 visit will take approximately 1 hr. to complete. Participants and their caregivers will return for a follow-up visit 4 weeks after discontinuing the investigational treatment. The assessment will include measurement of vital signs (height, weight, blood pressure, heart rate, and temperature), caregiver completion of behavioral outcome measures (SRS-2, RBSR, and ABC), and clinician-rated CGI-Severity and CGI-Improvement scores. The adverse event log will also be completed by the study physician. Caregivers will be asked to report any changes in concurrent medications or non-pharmacological treatments since the previous study visit. Treatment assignment (Avmacol® or placebo) will be obtained by study staff from IDS and shared with participants and their caregiver. Participants who were assigned to take placebo will have the opportunity to receive a 3-month supply of Avmacol® at no cost, supervised by the study physician under routine clinical care following study exit. Monetary compensation for study participation will be provided to participants and their caregiver in the form of 2 checks at the end of each clinic visit, as described in section 12.3 below.

7 Statistical Plan

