5.3 Method for Assigning Subjects to Treatment Groups

Enrolled participants will be stratified for age (13-18 and 19-30 years) to account for possible effects of age on treatment response. The goal is to recruit twenty-seven 13-18 year-olds and twenty-seven 19-30 year-olds to allow for separate analysis of adolescents and adults (exploratory). Individuals will be randomly assigned to treatment group within age strata by generating random numbers for each group for each entry (i.e., 1-27 for younger group and 1-27

for older group). The larger half of the random numbers within each group will be assigned to receive the treatment and the smaller half to the placebo condition. These two lists – listed in their original order (1-27 for younger and 1-27 for older) will be provided to UNC Investigational Drug Services (IDS) pharmacists. They will consult the list and provide the appropriate medication to each individual depending on the order in which they present to the pharmacy within their age group. Study personnel will remain blinded to treatment condition for the duration of the study.

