8.4 Unblinding Procedures

The study team will make every effort to maintain blinding of treatment assignment for both subject and investigator for the entire duration of the individual subject's study participation. Treatment unblinding will be limited to the occurrence of a serious adverse event (SAE) that the independent medical monitor determines is possibly related to study treatment and study participation. In the event of such an unanticipated problem, study staff will contact UNC IDS via the on-call [contact]) to report the occurrence of the event and request that treatment assignment status be disclosed to the independent medical monitor. The study staff and participant and caregiver will remain blinded to treatment. The treatment status will be faxed by IDS to the medical monitor and relevant medical personnel involved in treating the subject (e.g., emergency room physician, primary care physician). A narrative description of the SAE and treatment status will be documented in the CRF, and the FDA and UNC IRB will be promptly notified as specified above in Section 8.3.1.

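### Section 6.8 gives study staff each participant's code at his own Week 16 visit, against the blinding rules in 5.3, 5.8, 8.4 and Appendix 6B, and exposes clinician-rated outcomes to indirect unblinding

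*Combined protocol and SAP*

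**What the plan says.** **Section 6.8 (Week 16 visit).** The assignment "will be obtained by study staff from IDS and shared with participants and their caregiver". The sentence stands between that visit's assessments and that visit's payment. Placebo participants are then offered a three-month supply of Avmacol, "supervised by the study physician under routine clinical care following study exit".

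**Section 5.8.** "Blinding of treatment assignment for the study team and subjects will be maintained until after the conclusion of all data collection".

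**Section 5.3, repeated word for word in Appendix 6B.** "Study personnel will remain blinded to treatment condition for the duration of the study".

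**Section 8.4.** The first sentence promises the blind "for the entire duration of the individual subject's study participation". The next restricts unblinding to a serious adverse event that the independent medical monitor considers possibly related. Even in that case, "The study staff and participant and caregiver will remain blinded to treatment".

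**Who rates what.** SRS-2, RBSR and ABC are completed by caregivers. CGI-S and CGI-I are clinician-rated. Section 6.3 names the rater at baseline: "The study physician will complete the CGI-S to establish baseline clinical severity of ASD prior to intervention". Section 6.7 gives the Week 12 CGI ratings to unnamed clinicians. The study physician also reviews the screening laboratory results for eligibility and completes the adverse event log.

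**The concern.** Read plainly, 6.8 releases codes one participant at a time while the trial is still running. Staff who learn them go on to enrol, rate and assess later participants. The study physician, who supervises the post-study supply, also learns who had placebo among those who take it up. No section separates the CGI raters from staff who hold codes.

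One participant's code does not directly reveal another's. The leak is indirect, by two routes:

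- Allocation uses a fixed list of 27 slots per age stratum, so each disclosed code changes the odds for those that remain.
- Staff learn which patterns of response and adverse events went with active tablets.

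At stake are the CGI-S secondary hypothesis, the CGI-I response proportions, the CGI-I component of full and partial responder status, attribution of non-serious adverse events, and enrolment decisions.

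**Working it through.** **1. The text.** No stated figure is involved, so the first check sets the sections side by side.

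| Section | How long staff stay blinded | Compatible with 6.8? |
|---|---|---|
| 5.8 | Until all data collection has ended | No |
| 5.3 and Appendix 6B | For the duration of the study | No, on plain reading |
| 8.4, first sentence | For the individual's own participation | Yes |
| 8.4, later sentences | Unblinding only for a possibly related SAE, with staff still blinded | No |

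**2. Overlap of disclosure with ongoing ratings.** Inputs: 54 participants (3.1), 16 weeks each (3.1), study duration 24 months (Study Summary). The accrual period T is not stated. I take T = 88 weeks (88 + 16 = 104 weeks = 24 months), 60 and 40, with even spacing and no dropout. Participant *i* enrols at (i − 1) × T/53, and his code is released 16 weeks later.

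Example for T = 88: the spacing is 88/53 = 1.66 weeks. By week 16, floor(16/1.66) + 1 = 10 are enrolled, so 44 are not. A Week 12 rating precedes the first disclosure only if enrolment is by week 4: floor(4/1.66) + 1 = 3, so 51 come after it.

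| | T = 88 | T = 60 | T = 40 |
|---|---|---|---|
| Not yet enrolled at first disclosure | 44 | 39 | 32 |
| Week 12 rating still ahead at first disclosure | 51 | 50 | 48 |
| Codes known when the last participant enrols | 44 | 39 | 32 |
| Codes known at his Week 12 rating | 51 | 50 | 48 |
| Week 12 ratings made with at least 10 codes known | 42 | 41 | 39 |

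**3. What the remaining counts reveal.** Section 5.3 fixes 27 slots per stratum, so one arm has 14 and the other 13. Let the lag be the number of earlier participants in the stratum whose codes are not yet out. For the last participant's Week 12 rating it averages (53 − 51)/2 = 1.0, (53 − 50)/2 = 1.5 and (53 − 48)/2 = 2.5 for T = 88, 60 and 40. At his enrolment it averages 4.5, 7 and 10.5. The best guess is the arm with more slots left. The chance that it is right, averaged over random 14/13 lists:

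| Lag | Last nine, larger arm known | Last nine, larger arm not known | All 27, known / not known |
|---|---|---|---|
| 8 | 0.584 | 0.577 | 0.547 / 0.537 |
| 5 | 0.605 | 0.598 | 0.560 / 0.551 |
| 3 | 0.626 | 0.616 | 0.571 / 0.563 |
| 2 | 0.643 | 0.627 | 0.579 / 0.569 |
| 1 | 0.659 | 0.643 | 0.588 / 0.578 |
| No disclosure | 14/27 = 0.519 | 0.500 | 0.519 / 0.500 |

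Section 5.3 does not say which arm gets 14, so both cases are shown. Clues from symptoms or response are not included.

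**4. The participant's own data.** Section 8.1 keeps adverse event reporting open for 30 days after the last dose. Week 16 falls 4 × 7 = 28 days after stopping, so disclosure can come about two days before that window closes. Nor does 6.8 say that the code is fetched only after his Week 16 CGI ratings are complete.

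**The case against.** - **Per-participant use of the word study.** The protocol sometimes uses the word for one person's participation: 6.8 is headed Study Termination, and the schedule in Appendix 6A labels Week 16 as study end. On that reading 5.3 and Appendix 6B could fit 6.8, and 8.4 could be taken to govern emergencies within that period. This softens three of the conflicts. It does not help with 5.8, which is tied to the end of all data collection.
- **Raters may not be the staff who fetch codes.** The text uses separate labels for study staff, study physician and clinicians, so the overlap is inferred. That stands. But nothing keeps the groups apart, and the physician has a stated route to the codes of placebo participants who take the supply.
- **The last-nine figures show the worst segment.** True. Averaged over all 27, the guess rate is about 55-59% if the larger arm is known and 54-58% if not. The figures also assume full strata, no dropout (7.1 allows up to 15% loss) and a rater who tallies codes.
- **The primary is protected.** Agreed. Each caregiver is told only at Week 16, and relatedness of serious events is judged by an independent monitor. Most eligibility criteria are objective, so the enrolment risk is small.

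**Conclusion.** The concern holds. The conflict between 6.8 and 5.8 needs no assumption. Those with 5.3, Appendix 6B and the SAE restriction in 8.4 hold on plain reading; the first sentence of 8.4 is compatible with 6.8.

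Most ratings would follow some disclosure: 48 to 51 of the 54 Week 12 ratings over the accrual periods assumed. The gain in guessing from counts alone is modest on average and larger late in each stratum. It measures exposure under active tallying and does not show that ratings would be biased. The primary endpoint is not directly affected. This should be fixed because the clinician-rated secondary outcomes depend on a blind that the protocol both promises and breaks.

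**What to change.** Amend 6.8 so that no one who enrols participants, rates outcomes or assesses adverse events learns any individual code until data collection has ended for all participants, as 5.8 already requires. Bring 5.3, 8.4 and Appendix 6B to the same wording.

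If families are to be told sooner, have the investigational pharmacy inform them directly, after that participant's last ratings and after his 30-day adverse event window. Arrange access to the post-study supply so that raters do not learn the code.

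The cost is protocol wording, with no change to sample size or analysis. Families, including placebo participants offered the supply, may wait longer, or the pharmacy takes on a little more administration.
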